Type 4a: Myocardial infarction related to percutaneous coronary intervention (PCI) Myocardial infarction associated with PCI is arbitrarily defined by elevation of cTn values $>5 \times 99^{\text{th}}$ percentile URL in patients with normal baseline values ($<99^{\text{th}}$ percentile URL) or a rise of cTn values $>20\%$ if the baseline values are elevated and are stable or falling (*). In addition, either (i) symptoms suggestive of cardiac ischemia, or (ii) new ischemic ECG changes or new LBBB, or (iii) angiographic loss of patency of a major coronary artery or a side branch or persistent slow- or no-flow or embolization, or (iv) imaging demonstration of new loss of viable myocardium or new regional wall motion abnormality are required.

(*) In patients with normal baseline cTn, a clinically relevant MI postPCI is diagnosed by a new biomarker elevation of CK-MB to $\geq 10 \times \text{ULN}$ or cTn (I or T) to $\geq 70 \times \text{ULN}$ (or by CK-MB to $\geq 5 \times \text{ULN}$ or cTn to $\geq 35 \times \text{ULN}$ plus the development of new pathologic Qwaves in ≥ 2 contiguous leads or new LBBB). **[SCAI Definition]**

Type 4b: Myocardial infarction related to stent thrombosis

Myocardial infarction associated with stent thrombosis is detected by coronary angiography or autopsy in the setting of myocardial ischemia and with a rise and/ or fall of cardiac biomarkers values with at least one value above the 99th percentile URL.

Type 5: Myocardial infarction related to coronary artery bypass grafting (CABG)

Myocardial infarction associated with CABG is arbitrarily defined by elevation of cardiac biomarker values $>10 \times 99^{\text{th}}$ percentile URL in patients with normal baseline cTn values ($<99^{\text{th}}$ percentile URL). In addition, either (i) new pathological Q waves or new LBBB, or (ii)

angiographic documented new graft or new native coronary artery occlusion, or (iii) imaging evidence of new loss of viable myocardium or new regional wall motion abnormality.

REVASCULARISATION

[Target Lesion Revascularization (TLR)]

TLR is defined as any repeat percutaneous intervention of the target lesion or bypass surgery of the target vessel performed for restenosis or other complication of the target lesion. All TLR should be classified prospectively as clinically indicated [CI] or not clinically indicated by the investigator prior to repeat angiography. The target lesion is defined as the treated segment from 5 mm proximal to the stent and to 5 mm distal to the stent.

[Target Vessel Revascularization (TVR)]

TVR is defined as any repeat percutaneous intervention or surgical bypass of any segment of the target vessel. The target vessel is defined as the entire major coronary vessel proximal and distal to the target lesion which includes upstream and downstream branches and the target lesion itself

[Non Target Lesion Revascularization (Non-TLR)]

Any revascularization in the target vessel for a lesion other than the target lesion is considered a non-TLR.

[Non Target Vessel Revascularization (Non-TV)]

Revascularization of the vessel identified and treated as the non-target vessel at the time of the index procedure.

Note: TLR and TVR will be adjudicated by the Clinical Event Committee.

[Ischemia-driven Revascularization (CI-TLR/TV)]

A revascularization is considered clinically indicated if associated with any of the following:

- Positive functional ischemia study including positive FFR
- Ischemic symptoms and angiographic diameter stenosis $\geq 50\%$ by core laboratory QCA
- Angiographic diameter stenosis $\geq 70\%$ by core laboratory QCA without angina or positive functional study

[Coronary Artery Bypass Graft Surgery]

CABG during follow-up is only considered as a clinically-indicated target lesion revascularization if coronary angiography indicates a diameter of stenosis $\geq 50\%$ of the index lesion (core lab QCA assessment) associated with one of the following conditions:

- A positive history of recurrent angina pectoris presumably related to the target vessel
- Objective signs of ischemia (12-lead ECG, exercise test or equivalent) presumably related to the target vessel
- Abnormal results of any invasive functional diagnostic test (e.g. doppler flow velocity reserve, fractional flow reserve)

- A TLR/TVR with a diameter stenosis $\geq 70\%$ (core lab QCA assessment) in the absence of the above mentioned ischemic signs or symptoms

STENT THROMBOSIS

(ARC Circulation 2007; 115: 2344-2351)

Stent thrombosis should be reported as a cumulative value at the different time points and with the different separate time points. Time 0 is defined as the time point after the guiding catheter has been removed and the subject left the catheterization lab.

Timing:

- Acute stent thrombosis*: 0 - 24 hours post stent implantation
- Subacute stent thrombosis*: >24 hours - 30 days post stent implantation
- Late stent thrombosis†: 30 days - 1 year post stent implantation
- Very late stent/ thrombosis†: >1 year post stent implantation

* Acute/subacute can also be replaced by early stent thrombosis. Early stent thrombosis (0 - 30 days) - this definition is currently used in the community.

† Including “primary” as well as “secondary” late stent thrombosis; “secondary” late stent thrombosis is a stent thrombosis after a target segment revascularization.

Categories:

- Definite
- Probable
- Possible

Definitions of each category are as follows.

- **Definite stent thrombosis**

Definite stent thrombosis is considered to have occurred by either angiographic or pathologic confirmation.

Angiographic confirmation of stent thrombosis*

The presence of a thrombus[†] that originates in the stent or in the segment 5 mm proximal or distal to the stent and presence of at least one of the following criteria within a 48-hour time window:

- Acute onset of ischemic symptoms at rest
- New ischemic ECG changes that suggest acute ischemia
- Typical elevation or depression in cardiac biomarkers (refer to definition of spontaneous MI)
- Nonocclusive thrombosis
 - Thrombus Intracoronary thrombus is defined as a (spheric, ovoid, or irregular) noncalcified filling defect or lucency surrounded by contrast material (on 3 sides or within a coronary stenosis) seen in multiple

projections, or persistence of contrast material within the lumen, or a visible embolization of intraluminal material downstream.

- Occlusive thrombus
 - TIMI 0 or TIMI 1 in-stent or proximal to a stent up to the most adjacent proximal side branch or main branch (if originates from the side branch).
- * The incidental angiographic documentation of stent occlusion in the absence of clinical signs or symptoms is not considered a confirmed stent thrombosis.
- † Intracoronary thrombus.

Pathological confirmation of stent thrombosis

Evidence of recent thrombus within the stent determined at autopsy or via examination of tissue retrieved following thrombectomy.

- **Probable stent thrombosis**

Either of the following occurred after stent implantation will be considered a probable stent thrombosis:

- Any unexplained death within the first 30 days[‡]
- Irrespective of the time after the index procedure, any MI that is related to documented acute ischemia in the territory of the implanted stent without angiographic confirmation of stent thrombosis and in the absence of any other obvious cause

‡ For studies with ST-elevation MI population, one may consider the exclusion of unexplained death within 30 days as evidence of probable stent thrombosis.

- **Possible stent thrombosis**

Clinical definition of possible stent thrombosis is considered to have occurred with any unexplained death from 30 days following intracoronary stenting until end of trial follow up.

STROKE

[Cerebrovascular Accident (CVA) / Stroke]

Stroke is defined as a sudden onset of focal neurological deficits due to vascular lesions of the brain that persists >24 hours. Any neurological symptom that lasts < 24 hours is classified as transient ischemic attack (TIA). Stroke results from either of two types of cerebral vascular disturbance: ischemia or hemorrhage.

[Transient ischemic attack (TIA)]

TIA are focal neurologic abnormalities of sudden onset and brief duration (i.e., lasting less than 24 hours) that reflect dysfunction in the distribution of the affected artery. TIAs include transient monocular blindness (e.g., amaurosis fugax defined as a transient episode of monocular blindness, or partial blindness, lasting ten minutes or less) and transient hemispheric attacks.

TIMI FLOW GRADES

0. No contrast flow through the stenosis.
1. A small amount of contrast flows through the stenosis but fails to fully opacify the artery beyond.
2. Contrast material flows through the stenosis to opacify the terminal artery segment. However, contrast enters the terminal segment perceptibly more slowly than more proximal segments. Alternatively, contrast material clears from a segment distal to a stenosis noticeably more slowly than from a comparable segment not preceded by a significant stenosis.
3. Anterograde flow into the terminal coronary artery segment through a stenosis is as prompt as anterograde flow into a comparable segment proximal to the stenosis. Contrast material clears as rapidly from the distal segment as from an uninvolved, more proximal segment.

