- 2) Third Universal definition of MI (*European Heart Journal* (2012) 33, 2551–2567)

For peri-procedural MI an additional definition will be added: SCAI (*Catheter Cardiovasc Interv.* 2014 Jan 1;83(1):27-36)

NOTE: The primary endpoint for this trial (device-oriented composite endpoint, DOCE or TLF) will be assessed according WHO Extended Definition of MI!

1) [WHO Extended Definition]

I. PCI (Percutaneous Coronary Intervention)

Ia. Baseline Biomarkers of Myocardial Damage (CK and CKMB and Trop < 1*URL) *and* not acute MI in progress.

Periprocedural <48 hours post PCI

A. New pathologic q waves in ≥ 2 contiguous ECG leads **AND**

- any CKMB > 1*URL **or**
- in the absence of CKMB: Troponin > 1*URL **or**
- in the absence of CKMB and Troponin: CK > 1*URL **or**
- in the absence of CKMB and Troponin and CK: CEC decision upon clinical scenario

B. Appropriate cardiac enzyme data (respecting top-down hierarchy, b1 to b3):

b1. **CK $\geq 2^* URL$ Confirmed by:**

- **CKMB > 1*URL or**
- in the absence of CKMB: Troponin > 1*URL **or**
- in the absence of CKMB and Troponin: CEC decision upon clinical scenario

OR

b2. In the absence of CK: CKMB > 3*URL

OR

b3. In the absence of CK and CKMB: Troponin > 3*URL

Note URL = upper reference limit, defined as 99th percentile of normal reference range

Ib. If Baseline Biomarkers of Myocardial Damage: CK and/or CKMB > 1*URL *or* acute MI in progress.

Myocardial infarction, re-infarction (extension) <48 hours post PCI

A. If CK (or CKMB) from index MI has not yet reached its maximum level:

- Recurrent thoracic chest pain or ischemia equivalent >20 minutes (or new ECG changes consistent with MI)

AND

- Appropriate cardiac enzyme data:
- A rise in CK within 24 hours of the index event $>2^*\text{URL}$ (confirmed by either CKMB or Troponin $> 1^*\text{URL}$) and $\geq 50\%$ above the previous level **or**
- In absence of CK: a (post PCI) rise in CKMB within 24 hours of the index event $>3^*\text{URL}$ and $\geq 50\%$ above the previous level. **or**
- In absence of CK and CKMB: a (post PCI) rise of Troponin within 24 hours of the index event $>3^*\text{URL}$ and $\geq 50\%$ above the previous level.

B. If elevated CK (or CKMB) following the index MI has peaked **AND** CK level has returned $< \text{URL}$ then any new rise in:

- CK $>2^*\text{URL}$ (confirmed by either CKMB $> \text{URL}$ or Troponin $> \text{URL}$) **or**
- in the absence of CK: CKMB $> 3^*\text{URL}$ **or**

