- in the absence of CK and CKMB, Troponin $> 3^*\text{URL}$

C. If CK (or CKMB) following the index MI has peaked **AND** CK level has NOT returned $< \text{URL}$:

- A rise in CK $\geq 50\%$ above the previous level and $> 2 \text{ URL}$ confirmed by either CKMB $> \text{URL}$ or Troponin $> \text{URL}$. **or**
- In absence of CK, when CKMB has NOT returned $< \text{URL}$, a rise in CKMB $\geq 50\%$ above the previous level and $> 3 \text{ URL}$. **or**
- In absence of CK, when CKMB and Troponin has not returned $< \text{URL}$ a rise in Troponin $\geq 50\%$ above the previous level and $>3^*\text{URL}$

Spontaneous MI >48 hours(PCI)

A. Recurrent thoracic chest pain or ischemic equivalent **AND**

New pathologic q waves in ≥ 2 contiguous ECG leads **AND** :

- any CKMB $> 1^*\text{URL}$ **or**
- in the absence of CKMB: Troponin $> 1^*\text{URL}$ **or**
- in the absence of CKMB and Troponin: CK $> 1^*\text{URL}$ **or**
- in the absence of CKMB and Troponin and CK: CEC decision upon clinical scenario

B. Appropriate cardiac enzyme data:

b1. CK $\geq 2^*\text{URL}$ Confirmed by:

- CKMB $> 1^*\text{URL}$ **or**
- in the absence of CKMB: Troponin $> 1^*\text{URL}$ **or**
- in the absence of CKMB and Troponin: CEC decision upon clinical scenario

OR

b2. In the absence of CK: CKMB $> 3^*\text{URL}$

OR

b3. In the absence of CK and CKMB: Troponin $> 3^*\text{URL}$

OR

b4. In the absence of CK, CK-MB and Troponin, clinical decision based upon clinical scenario.

II. CABG (Coronary Artery Bypass Grafting)

IIa. Baseline Biomarkers of Myocardial Damage (CK and CKMB and Trop < 1*URL) *and* not acute MI in progress.

Periprocedural <72 hours post CABG

A. New pathologic q waves in ≥ 2 contiguous ECG leads or recurrent signs or symptoms consistent with myocardial ischemia **AND** :

- CK-MB >5x URL **or**
- in the absence of CKMB: Troponin > 5*URL **or**
- in the absence of CKMB and Troponin: CK > 5 URL **or**
- in the absence of CKMB and Troponin and CK: CEC decision upon clinical scenario

B. Appropriate cardiac enzyme data:

- CKMB $\geq 10^*$ URL **or**
- In the absence of CKMB: Trop > 10*URL. **or**
- In the absence of CKMB and Troponin: CK > 10*URL

IIb If Baseline Biomarkers of Myocardial Damage: CK and/or CKMB > 1*URL *or* acute MI in progress

Myocardial infarction, re-infarction (extension) <72 hours post CABG

A. If peak CK (or CKMB) from index MI has not yet reached its maximum level:

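### Does the WHO Extended MI definition leave patients with an isolated raised troponin, or with undrawn baseline markers, without a branch?

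*Combined protocol and SAP*

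**What the plan says.** Appendix II fixes the MI definition behind the primary endpoint: "NOTE: The primary endpoint for this trial (device-oriented composite endpoint, DOCE or TLF) will be assessed according WHO Extended Definition of MI". For PCI, that definition first sorts patients by baseline.

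- Ia (normal baseline): "Baseline Biomarkers of Myocardial Damage (CK and CKMB and Trop < 1*URL) *and* not acute MI in progress".
- Ib (raised baseline): "Ib. If Baseline Biomarkers of Myocardial Damage: CK and/or CKMB > 1*URL *or* acute MI in progress".
- For CABG, IIa repeats the first line ("IIa. Baseline Biomarkers of Myocardial Damage (CK and CKMB and Trop < 1*URL) *and* not acute MI in progress") and IIb repeats the second.

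The criteria applied after entry have fallbacks for missing markers, for example "In the absence of CK and CKMB: Troponin > 3*URL". The entry lines have none.

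Section 8.3 and note 3 of Appendix I leave the choice of markers before the index PCI to local routine and only prefer all three. Section 8.9 requires all three afterwards. Section 12.4 has the CEC classify MI by the protocol definitions. It also requires a CEC charter, written before the committee starts work, that covers the minimum data and the algorithm for classifying events.

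**The concern.** Troponin is tested in Ia but left out of Ib. A patient whose only raised baseline marker is troponin, with no acute MI in progress, fails both lines. A patient with an undrawn marker and nothing raised enters Ia only if the missing value is ignored, and the text does not say whether it may be. The population includes acute coronary syndromes, so an isolated raised troponin at baseline is foreseeable.

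The branches also differ in what they ask for. Ia can count an MI on enzyme level alone. Ib-A adds symptoms or ECG change, and both Ib-A and Ib-C add a rise of at least 50% over the previous level. The branch could therefore decide whether a peri-procedural MI counts towards TLF. If such events were more frequent in one arm, the way they are routed could shift the non-inferiority comparison.

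**Working it through.** The plan gives no figure on this point, so the check is to list the baseline states and trace each through the entry lines.

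**1. All three markers drawn, none exactly at URL.** There are 2³ × 2 = 16 combinations, counting acute MI in progress as yes or no. All 8 with acute MI enter Ib. Of the other 8:

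- Ib (CK or CKMB raised): 8 − 1 × 1 × 2 = 6
- Ia (all below URL): 1
- neither: 8 − 6 − 1 = 1, namely CK and CKMB below URL with troponin above

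No combination enters both.

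**2. Markers may be undrawn, no acute MI in progress.** There are 3³ = 27 states.

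| Baseline state | Count | Branch |
|---|---|---|
| CK or CKMB raised | 27 − 2 × 2 × 3 = 15 | Ib |
| All three drawn and below URL | 1 | Ia |
| Nothing raised, at least one undrawn | 2³ − 1 = 7 | Ia only if undrawn markers are ignored |
| Troponin raised, CK and CKMB each normal or undrawn | 2 × 2 = 4 | Neither, on any reading |

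The sum is 15 + 1 + 7 + 4 = 27. One of the seven is the state with nothing drawn. Section 8.3 lists the draw among the activities for all patients, so that state is arguably a deviation and not something the plan allows for.

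**3. Values exactly at URL.** Replacing undrawn with at URL also gives 27 states: 15 in Ib, 1 in Ia and 11 in neither, which is 10 more than the single state in step 1. This is a boundary slip of < against >.

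**4. What depends on the branch.** Ib-A, Ib-B and Ib-C all refer to CK or CKMB from an index MI; Ib-B, for instance, starts from "If elevated CK (or CKMB) following the index MI has peaked AND CK level has returned". A patient with measured normal CK and CKMB and no index MI has no such peak, so none of the three fits literally. The text therefore gives no reliable count of verdicts that would differ between branches. The routing bears only on the peri-procedural window (48 hours after PCI, 72 hours after CABG). Spontaneous MI after 48 hours reads as a separate block with no baseline condition, and cardiac death and clinically indicated TLR do not use these lines.

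**5. Between arms.** Let *s* be the share of patients in the gap, and *q*M and *q*X the proportions of them, in the MISTENT and XIENCE arms, whose verdict depends on the branch. With one rule for both arms, the TLF difference moves by *s*(*q*M − *q*X), which is zero when the two proportions are equal. The markers are drawn before the PCI and allocation is 1:1 in blocks by centre (8.4), so *s* balances in expectation.

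The documents give neither *s* nor *q*. As an assumption only, take *s* from 5% to 20% and *q* from 1% to 10%, equal in both arms:

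- low: 1400 × 0.05 × 0.01 = 0.7 patients, or 0.05 points of TLF
- high: 1400 × 0.20 × 0.10 = 28 patients, or 2.0 points

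Power is Φ(0.04/√(2p(1 − p)/682) − 1.645). At the planned p = 0.083 this is 84.9%, against the stated 85%. Counting the extra events gives 84.7% at p = 0.0835 and 78.4% at p = 0.103. A shared shift changes precision and leaves the difference between arms where it was.

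**The case for a change.** The strongest case for acting is that the defect is in print and in the definition behind the primary endpoint. The drafters wrote fallbacks for missing markers into the event criteria and none into the entry lines. The charter is not among the documents, and the CEC must follow the protocol definitions, so one cannot assume that it fills the hole. Acute MI in progress is not defined, and Ib fits badly once a troponin-only patient is placed there. Section 8.5.1 does not say whether the CEC is blinded, so routing case by case would be unwelcome.

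The textual gap stands, and it is true that the charter's content cannot be checked here. Less stands on consequence.

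- No wrong result and no difference between arms is shown. A count of net extra events needed to cross the margin would apply to any misclassification in the trial and does not measure this one.
- Comparing verdicts under Ia and Ib-B does not help, because Ib-B presupposes a CK or CKMB peak after an index MI.
- Section 8.3 and note 3 concern only the draw before the index PCI, so they do not conflict with IIa and IIb, which concern a later CABG.
- The charter's required content is this kind of routing, and it must exist before any event is classified.
- MI is also adjudicated by the Third Universal Definition, whose Type 4a criterion covers raised baseline troponin that is stable or falling. That gives a second reading of many of these cases.

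**Conclusion.** The entry lines are not exhaustive: 4 of 27 baseline states without acute MI in progress reach no branch, and 7 more depend on how an undrawn marker is read. This is missing detail that an adjudication committee fills sensibly, and the protocol names the document in which it does so. No change to the plan follows.

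The conclusion rests on two assumptions: that the charter routes these patients by one rule fixed before adjudication, and that the rule is the same in both arms. If so, the routing can move the arms apart only through a real difference in peri-procedural events within the affected group. The size of any effect on TLF cannot be derived from the documents, and the range above is assumed. Rewriting the definition would also gain little at this stage. Version 2.0 extends follow-up in the light of early results, so a new primary MI rule now would be post hoc.
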